Appendix 3. ICD codes and operational definition of adverse events

	Adverse events	ICD codes	Operational definition
1	Nasopharyngitis	ICD9: 472.2, 460 ICD10: J31.1, J00	Inpatient or outpatient (including ER visit) diagnosis.
2	Pneumonia	ICD9: 480-486, 487.0 ICD10: J10.0, J11.0, J12- J18,	 Primary inpatient diagnosis Inpatient diagnosis.
3	Moderate COPD exacerbation	ICD9: 491.x, 492.x, 496 ICD10: J41.x, J42, J43.x, J44.x	Outpatient diagnosis plus a prescription for oral corticosteroid or antibiotic for respiratory infection
4	Severe COPD exacerbation	ICD9: 491.x, 492.x, 496 ICD10: J41.x, J42, J43.x, J44.x	Inpatient or ER visits with a primary diagnosis.
5	Arrhythmia	ICD9: 427.x ICD10: I47.x, I48.x, I49.x	Inpatient or outpatient (including ER visit) diagnosis.
6	Myocardial ischemia	ICD9: 410.x, 411.x, 413.x ICD10: I20.x, I21.x, I22.x, I23.x, I24.x	Inpatient or outpatient (including ER visit) diagnosis.
7	Supraventricular tachycardia	ICD9: 427.0 ICD10: I47.1	Inpatient or outpatient (including ER visit) diagnosis.
8	Constipation	ICD9: 564.0, 564.00, 564.09 ICD10: K59.0, K59.00, K59.09	Inpatient or outpatient (including ER visit) diagnosis.
9	Diarrhoea	ICD9: 787.91 ICD10: R19.7	Inpatient or outpatient (including ER visit) diagnosis.
10	Urinary retention	ICD9: 788.2, 788.20, 788.29 ICD10: R33.x	Inpatient or outpatient (including ER visit) diagnosis.
11	Urinary tract infection	ICD9: 590, 595, 601, 604 ICD10: N10, N12, N15.1, N30.0, N30.8, N30.9, N41.0, N41.2, N41.3, N39.0	 Primary inpatient diagnosis Inpatient diagnosis. Either inpatient diagnosis or at least 2 outpatients (including ER visit) diagnosis; diagnostic interval within 30 days.
12	Urticaria	ICD9: 708.x ICD10: L50.x	Inpatient or outpatient (including ER visit) diagnosis.
13	Rash	ICD9: 782.1 ICD10: R21	Inpatient or outpatient (including ER visit) diagnosis.

Statistical and Epidemiological Analysis Plan (SEAP) for Non-Interventional Studies (NIS) Template

c40431892-01 Page 31 of 38

14	Glaucoma	ICD9: 365.x	Inpatient or outpatient
		ICD10: H40.x	(including ER visit) diagnosis
			from ophthalmologist.
15	Nonfatal myocardial	ICD9: 410.x, 411.x	1. Primary inpatient diagnosis
	infarction	ICD10: I21.x, I22.x, I23.x	+ hospital discharge
			without death certificates
			2. Inpatient diagnosis +
			hospital discharge without
			death certificates
16	Nonfatal hemorrhagic stroke	ICD9: 430, 431, 432.x	1. Primary inpatient diagnosis
		ICD10: 160.x, 161.x, 162.x	+ hospital discharge
			without death certificates

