Appendix 5. Drugs of interest

Groups	ATC code		
Use of other respiratory drugs			
Mucolytics	R05CB, R05CB01, R05CB02, R05CB03, R05CB04, R05CB05,		
	R05CB06, R05CB10, R05CB11, R05CB91, R05CB92		
Theophylline	R03DA04, R03DA54, R03DA74, R03DB04		
SABA	R03AC02, R03AC03, R03AC04, R03AC06		
SAMA	R03BB01		
SABA/SAMA	R03AL01, R03AL02		
Drugs for COPD exac	cerbation treatment		
Oral corticosteroid	H02AB01, H02AB02, H02AB04, H02AB05, H02AB06, H02AB08,		
	H02AB10, H02BX, H02BX91		
Antibiotic for COPD	J01AA02, J01CA04, J01CR02, J01CR05, J01EE01, J01DC01,		
exacerbation	J01DC02, J01DC03, J01DC04, J01DC05, J01DC06, J01DC07,		
	J01DC09, J01DC14, J01DD01, J01DD02, J01DD04, J01DD05,		
	J01DD06, J01DD07, J01DD08, J01DD12, J01DD13, J01DD14,		
	J01DD52, J01DD62, J01DE01, J01DE02, J01FA01, J01EA02,		
	J01EA03, J01EA06, J01EA07, J01EA08, J01FA09, J01FA10,		
	J01FA15, J01FA91, J01MA01, J01MA02, J01MA03, J01MA04,		
	J01MA06, J01MA07, J01MA09, J01MA12, J01MA14, J01MA15		
Drugs for Medication	history		
Cardiovascular d	Irugs		
Anti-hypertensives	C02AA01, C02AA02, C02AA04, C02AB01, C02AB02, C02AC01,		
	C02CA01, C02CA04, C02CA, C02CC02, C02DA01, C02DB02,		
	C02DC01, C02DD01, C02LA01, C02LA50, C02LA51, C02LB01,		
	C02LG02, C02N, C03AA01, C03AA03, C03AA06, C03AA07,		
	C03AA, C03BA04, C03BA08, C03BA11, C03CA01, C03CA02,		
	C03CA04, C03CC01, C03DA01, C03DA04, C03DB01, C03DB02,		
	C03EA01, C03EA, C07AA01, C07AA02, C07AA03, C07AA05,		
	C07AA06, C07AA07, C07AA12, C07AA15, C07AA19, C07AB02,		
	C07AB03, C07AB04, C07AB05, C07AB07, C07AB09, C07AB12,		

Statistical and Epidemiological Analysis Plan (SEAP) for Non-Interventional Studies (NIS) Template

c40431892-01 Page 34 of 38

1 2	C07AC01 C07AC02 C07DAC0 C07DD02 C07CA02 C07CD02
	C07AG01, C07AG02, C07BA68, C07BB02, C07CA03, C07CB03,
	C07DA06, C08CA01, C08CA02, C08CA03, C08CA04, C08CA05,
	C08CA07, C08CA08, C08CA09, C08CA12, C08CA13, C08CA15,
	C08DA01, C08DB01, C09AA01, C09AA02, C09AA03, C09AA04,
	C09AA05, C09AA06, C09AA07, C09AA08, C09AA09, C09AA16,
	C09BA01, C09BA02, C09BA04, C09BB04, C09BB05, C09BB,
	C09BB, C09CA01, C09CA02, C09CA03, C09CA04, C09CA06,
	C09CA07, C09CA08, C09CA09, C09DA01, C09DA03, C09DA04,
	C09DA06, C09DA07, C09DA08, C09DA09, C09DB01, C09DB02,
	C09DB04, C09DB07, C09DX01, C09DX03, C09DX04, C09XA02,
	C09XA52, C09XA53, C09XA54
Antiarrhythmics	C01AA04, C01AA05, C01AA07, C01AA08, C01AB01, C01AC01,
	C01BA01, C01BA02, C01BA03, C01BA04, C01BA08, C01BB01,
	C01BB02, C01BC03, C01BC04, C01BD01, C01BD07, C01CA02,

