Antibacterials for	J01AA01, J01AA02, J01AA03, J01AA04, J01AA06, J01AA07,
systemic use	J01AA08, J01AA09, J01AA12, J01AA56, J01BA01, J01BA02,
	J01BA51, J01CA01, J01CA02, J01CA03, J01CA04, J01CA06,
	J01CA08, J01CA09, J01CA10, J01CA12, J01CA13, J01CA14,
	J01CA15, J01CA16, J01CA18, J01CA20, J01CA91, J01CE01,
	J01CE02, J01CE08, J01CE09, J01CE30, J01CF01, J01CF02,
	J01CF04, J01CF05, J01CG01, J01CR01, J01CR02, J01CR03,
	J01CR04, J01CR05, J01CR50, J01CR50, J01CR50, J01DB01,
	J01DB02, J01DB03, J01DB04, J01DB05, J01DB06, J01DB07,
	J01DB08, J01DB09, J01DC01, J01DC02, J01DC03, J01DC04,
	J01DC05, J01DC06, J01DC07, J01DC09, J01DC14, J01DD01,
	J01DD02, J01DD04, J01DD05, J01DD06, J01DD07, J01DD08,
	J01DD12, J01DD13, J01DD14, J01DD52, J01DD62, J01DE01,
	J01DE02, J01DF01, J01DH02, J01DH03, J01DH04, J01DH51,
	J01DI02, J01DI54, J01E, J01EA01, J01EB01, J01EB02, J01EB05,
	J01EB06, J01EB20, J01EC, J01EC01, J01EC02, J01EC20,
	J01ED01, J01ED05, J01ED20, J01EE01, J01FA01, J01EA02,
	J01EA03, J01EA06, J01EA07, J01EA08, J01FA09, J01FA10,
	J01FA15, J01FA91, J01FF01, J01FF02, J01GA01, J01GB01,
	J01GB03, J01GB04, J01GB05, J01GB06, J01GB07, J01GB08,
	J01GB09, J01GB11, J01MA01, J01MA02, J01MA03, J01MA04,
	J01MA06, J01MA07, J01MA09, J01MA12, J01MA14, J01MA15,
	J01MB01, J01MB02, J01MB03, J01MB04, J01MB08, J01RA02,
	J01XA01, J01XA02, J01XB, J01XB01, J01XC01, J01XD01,
	J01XD02, J01XD03, J01XE, J01XE01, J01XE02, J01XX01,
	J01XX04, J01XX05, J01XX07, J01XX08, J01XX09, J01XX91
Antimycotics for	J02AA01, J02AB01, J02AB02, J02AC01, J02AC02, J02AC03,
systemic use	J02AC04, J02AC05, J02AX01, J02AX04, J02AX05, J02AX06
Antimycobacterials	J04AA03, J04AB01, J04AB02, J04AB03, J04AB04, J04AB91,
	J04AC01, J04AC51, J04AD01, J04AK01, J04AK02, J04AK04,
	J04AM02, J04AM03, J04AM05, J04AM06, J04AM07, J04BA01,
	J04BA02

Statistical and Epidemiological Analysis Plan (SEAP) for Non-Interventional Studies (NIS) Template

c40431892-01 Page 37 of 38

Antineoplastic age	ents
Alkylating agents	L01AA01, L01AA02, L01AA03, L01AA06, L01AA09, L01AB01,
	L01AC01, L01AC03, L01AD01, L01AD02, L01AD06, L01AX03,
	L01AX04
Antimetabolites	L01BA01, L01BA04, L01BA05, L01BB02, L01BB03, L01BB04,
	L01BB05, L01BB06, L01BC01, L01BC02, L01BC03, L01BC05,
	L01BC06, L01BC07, L01BC53, L01BC59
Plant alkaloids and	L01CA01,L01CA02, L01CA04, L01CB01, L01CD01, L01CD02,
other natural products	L01CE01, L01CE02
Cytotoxic antibiotics	L01DA01, L01DB01, L01DB02, L01DB03, L01DB04, L01DB06,
and related substances	L01DB07, L01DC01, L01DC03, L01DC04

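### Five antibiotic ATC codes in SAP Appendix 5 appear mistyped and feed the moderate COPD exacerbation outcome; the UTI and nonfatal MI code lists need a crosswalk check.

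*SAP*

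**What the plan says.** **Antibiotics.** SAP Appendix 3 row 3 defines a moderate COPD exacerbation as "Outpatient diagnosis plus a prescription for oral corticosteroid or antibiotic for respiratory infection". SAP 7.2.2 uses the same rule for the baseline exacerbation covariate. The qualifying antibiotics are in Appendix 5, under the drugs for treating exacerbation. After J01FA01 and J01EA02 that list continues "J01EA03, J01EA06, J01EA07, J01EA08, J01FA09, J01FA10". The separate list of systemic antibacterials, used for the medication history in Table 3, reads "J01ED01, J01ED05, J01ED20, J01EE01, J01FA01, J01EA02" and goes on through the same four further J01EA codes to J01FA09. Earlier in that second list stands "J01DI02, J01DI54, J01E, J01EA01, J01EB01, J01EB02, J01EB05".

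**Urinary tract infection.** Appendix 3 row 11 gives "ICD9: 590, 595, 601, 604 ICD10: N10, N12, N15.1, N30.0, N30.8, N30.9, N41.0, N41.2, N41.3, N39.0". By contrast, the constipation row gives subcodes on both sides: "ICD9: 564.0, 564.00, 564.09 ICD10: K59.0, K59.00, K59.09".

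**Nonfatal MI.** Appendix 3 row 15 sets ICD-9 410.x and 411.x against "ICD10: I21.x, I22.x, I23.x". The myocardial ischemia row has "ICD9: 410.x, 411.x, 413.x ICD10: I20.x, I21.x, I22.x, I23.x, I24.x". Appendix 4 row 2 (cardiovascular disease) covers ICD-9 410-414 and, within the same part of ICD-10, I20-I22, I24 and I25, without I23.

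**Coding switch.** SAP section 8 places the change from ICD-9-CM to ICD-10-CM at 1 January 2016, inside the 2014-2019 study period. The Table 2 shell has one rate per event for the whole period.

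**The concern.** The protocol's ENCePP checklist leaves the coding of exposure, outcomes and covariates to the SEAP, and SAP 7.2.1 refers to the Annex for the operational definitions. These lists therefore are the outcome definitions, and no other visible text would correct a wrong code. A second analyst who repeats the programming would inherit the same list. Section 6.1 also says individual-level data cannot leave the data centre for independent verification.

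If the five codes are mistyped, a visit whose only qualifying drug carries one of the intended codes is not counted as a moderate exacerbation, in any study year. That touches the moderate row of Table 2 and the baseline moderate and all-exacerbation rows of Table 3. The same slip in the second list touches only the antibiotic-history row of Table 3.

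The ICD question is separate. If a list captures different diagnoses before and after 2016, the single 2014-2019 rate pools two definitions. For MI this would also apply to the risk set, because SAP 7.2.1 excludes patients with the condition at baseline.

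**Working it through.** The plan states no figure for this point, so the check compares the lists with themselves and with each other.

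**1. Order of the antibiotic codes.** I read each list from first to last and counted the places where a code sorts below the one before it.

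| Appendix 5 list | Entries | Breaks as printed | Breaks if the five are read as J01FA |
|---|---|---|---|
| Exacerbation antibiotics | 48 | 2: J01EE01→J01DC01, J01FA01→J01EA02 | 1: J01EE01→J01DC01 |
| Systemic antibacterials (history) | 157 | 1: J01FA01→J01EA02 | 0 |

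The five codes are J01EA02, 03, 06, 07 and 08. They fill the gap between J01FA01 and J01FA09 in both lists. J01EA01 stands between J01E and J01EB01 in the history list, where further J01EA codes would belong. The neighbouring codes J01FA01, 09, 10, 15 and 91 read correctly in both lists, so a random PDF misreading of exactly these five, twice, is unlikely.

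**2. What is left if they are wrong.** 48 − 5 = 43 other antibiotics still qualify a visit, as does any listed oral corticosteroid. The five are 5/48 = 10.4% of the exacerbation codes and 5/157 = 3.2% of the history entries. These are shares of codes, not of prescriptions. The SAP counts each patient's first event, so a missed visit may only delay the counted event if a later visit qualifies. Severe exacerbation (row 4) uses no antibiotic list and is unaffected.

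**3. UTI row.** The ICD-9 side has four categories with no subcodes (590, 595, 601, 604). The ICD-10 side has ten codes in six categories (N10, N12, N15, N30, N39, N41), with selection inside N30 (.0, .8, .9) and N41 (.0, .2, .3). The level of detail differs. Which diagnoses are gained or lost cannot be read from the SAP, because it prints no code descriptions.

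**4. Nonfatal MI row.** Suppose row 15 and Appendix 4 row 2 were both parallel.
- Row 15 would make I23 a partner of 410 or 411.
- Appendix 4 row 2 contains 410 and 411 (410-414), so it would need I23.
- It lists only I20-I22, I24 and I25.

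They cannot both be parallel. The argument does not say which one is wrong.

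**5. Weight of the ICD-9 years.** Protocol 9.5 assumes uniform entry over 6 years; 2014-2015 are the first 2.
- Follow-up to end 2019 for everyone (assumed): (2²/2)/(6²/2) = 2/18 = 11.1% of person-time.
- Very short follow-up (limit): 2/6 = 33.3%.
- No use before 2016 (assumed; SAP 9.3 mentions years without coverage): about 0%.

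With share s, and an ICD-9-era rate wrong by a fraction e relative to the ICD-10 definition when the true rate is constant, the pooled rate moves by s × e. For an assumed e = 10%: 0.111 × 10% = 1.1%, to 0.333 × 10% = 3.3%, or about 0. The documents give no value for e.

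**The case against.** **On the antibiotics.** Confirmation needs the ATC index, and the exacerbation list is not in strict order anyway, since J01EE01 precedes J01DC01. Both points are true. The second does not weaken the pattern: the longer list is otherwise in order throughout, and its only break is at the same five codes. The objection that the effect is bounded by the 43 other antibiotics and oral corticosteroids stands. So does the objection that protocol Table 1 offers no yardstick: its 55.42 per 100 patient-years is for undivided COPD exacerbation, whereas the antibiotic list feeds only the moderate row.

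**On UTI.** ICD-9 and ICD-10 are built differently, so unequal counts prove nothing. Bare codes elsewhere in the SAP (480-486 for pneumonia, 250 for diabetes) read as whole categories, and the urinary retention row pairs selected ICD-9 subcodes with all of R33.x. This stands. A reader might infer that the UTI lists differ in clinical scope, that N39.0 lacks an ICD-9 partner, or that 604 lacks an ICD-10 one. The documents do not show any of these.

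**On MI.** A reader might infer that the ICD-9 side of row 15 is broader than its ICD-10 side because 411.x is kept while I20 and I24 are dropped relative to row 6. That does not follow. If 411 pairs with I23, and 413 with I20 and I24, row 15 is consistent and the gap lies in Appendix 4, a baseline comorbidity list. Only the incompatibility of the two lists is established.

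**On era checks.** Protocol 9.7.2 and SAP 10.2 are not visible, and the checklist cites 9.7.2 for stratified and sensitivity analyses. An era split may already be planned.

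**Conclusion.** The antibiotic point holds on the documents: five codes in a list that defines a primary outcome are very probably mistyped, and the same five are wrong in the history list. If so, literal use loses some moderate exacerbations, at baseline and during follow-up, in all years. The size is unknown and may be small. A reader might go further and call the exacerbation rate materially biased, but nothing in the documents gives the share of visits that depend on these codes alone.

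The ICD point holds only as a query. The UTI row is uneven in detail, and the MI row and Appendix 4 row 2 are mutually inconsistent. Neither the faulty list nor the direction is shown. Any effect on the pooled rate is scaled by the ICD-9 share of person-time, which is 11% to 33% under uniform entry and near zero if use began in 2016.

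**What to change.** Before analysis:

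1. Check J01EA02, 03, 06, 07 and 08 against the ATC index and the source file. If the error is confirmed, change them to the J01FA codes in both Appendix 5 lists.
2. Check Appendix 3 rows 11 and 15 and Appendix 4 row 2 against an ICD-9-CM/ICD-10-CM crosswalk. Reconcile them or state the reason for each difference. Which codes to add or drop should follow from the crosswalk and not be fixed in advance. Apply the settled MI list to both the event and the baseline exclusion.
3. If the sections not shown do not already provide it, report UTI and nonfatal MI rates for 2014-2015 and 2016-2019 next to the pooled rate.

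The cost is one index and crosswalk check, edits to the SAP annex and at most a small table addition. No new data are needed.

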Appendix 4. ICD codes and operational definition of comorbidities

	Comorbidities:	ICD codes	Operational definition
1.	Diabetes	ICD9: 250	Either inpatient diagnosis or
		ICD10: E10.x-E11.x	more than twice outpatient
			diagnosis
2.	Cardiovascular disease	ICD9: 250.7, 401-405,	Either inpatient diagnosis or
		410-414, 425-428, 429.1-	more than twice outpatient
		429.3, 441, 442, 458	diagnosis
		ICD10: E10.5x, E11.5x,	
		I10-I13.x, I15.x, I20.x-	
		122.x, 124.x, 125.x, 142.x-	
		144, 145.xx, 146.x-149.x,	
		I50.xx, I51.5, I51.7, I51.9,	
		171.xx, 179.0, 172.x,	
		177.7x, 195.x	
3.	Cerebrovascular disease	ICD9: 430-438	Either inpatient diagnosis or
			more than twice outpatient
		166.x, G45.x, G46.x, 167.x-	diagnosis
		169.x	
4.	Cancer	ICD9: 140-199, 200-208	Inpatient diagnosis.
		ICD10: C00-C26, C30-34,	
		C37-39, C40-41, C43-49,	
		C4A, C50-58, C60-69,	
		C70-79,C7A, C7B, C80-	
		86, C88, C90-96,	
5.	Chronic kidney disease	ICD9: 585-587,	Either inpatient diagnosis or
		ICD10: N18-19, N26.1,	more than twice outpatient
		N26.9	diagnosis
6.	Pneumonia	ICD9: 480-486, 487.0	Inpatient diagnosis
		ICD10: J10.0, J11.0, J12-	
		J18,	
7.	Cirrhosis		Either inpatient diagnosis or
		ICD10: K70.3x, K74.3,	more than twice outpatient
		K74.4, K74.5, K74.6x	diagnosis

Statistical and Epidemiological Analysis Plan (SEAP) for Non-Interventional Studies (NIS) Template

c40431892-01 Page 33 of 38

Proprietary confidential information © 2022 Boehringer Ingelheim International GmbH or one or more of its affiliated companies

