	2. Individuals with asthma, allergic rhinitis, lung cancer, interstitial lung disease, or lung transplant identified at any time prior to the index date.		
Variables:	Exposures:		
	-		initiation of period between 1st January
	Outcomes:		
	Primary outcome:		
	• Incidence rate of adverse events in patients with COPD treated with Tio+Olo		
	Secondary outcom	nes:	
	To describe the baseline characteristics of patients who initiated Tio+Olo;		

NIS Protocol Page 12 of 43 BI Study Number: 1237-0109 c38644780-01

Name of company:			
Boehringer Ingelheim			
Name of finished n	nedicinal		
product:			
Spiolto Respimat			
Name of active ing			
Tiotropium + Oloda	terol {R03AL06}		
Protocol date:	Study	Version/Revision:	Version/Revision date:
11 May 2022	number:		
	1237.0109	1.0	NA
	1		cs of patients who initiated
			r LAMA/LABAs in the Taiwan
	NHIRD databa	se;	
	Covariates:		
		•	ort entry, season of index date
	(winter, spring, summer, fall)		
	Additional charact	teristics will be define	d during the 1 year pre-index
	baseline period:		
	specific previous	COPD treatments, prev	vious COPD exacerbation,
	hospitalizations caused by exacerbation of heart failure, all-cause		of heart failure, all-cause
	hospitalizations, comorbidities, Charlson Comorbidity Index (CCI),		
	history of medications dispensed.		
Data sources:	Determined in this starter will some first A. T. i. N. C. 111, 14		
	Data used in this study will come from the Taiwan National Health		
	Insurance (NHI) claims data between 2014 and 2019.		
	Data sources include Taiwan NHI, Taiwan cancer registry (TCR) and Taiwan Mortality Data. Taiwan Department of Statistics, Ministry of		
			by the government to
			cal databases, and to develop
	data platform for academic research. Through the services provided by		
	the Health and Welfare Data Science Center (HWDSC) of the		
	 	-	access a wide range of health lity (with cause of death) and
		gistry (TCR). The HW	• •
	-	individuals according t	* *
	algorithm that is no	ot made known to the p	oublic. The encrypted ID is
		iduals and will be used	d for linkage between
	databases.		

NIS Protocol Page 13 of 43 BI Study Number: 1237-0109 c38644780-01

Proprietary confidential information © 2022 Boehringer Ingelheim International GmbH or one or more of its affiliated companies				
Name of company:				
Boehringer Ingelhei	m			
Name of finished n	nedicinal			
product:				
Spiolto Respimat				
Name of active ing				
Tiotropium + Oloda	iterol {R03AL06}			

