9.9 LIMITATIONS OF THE RESEARCH METHODS

In this study, we will describe the incidence rate of AEs among patients who initiate Spiolto. Patients taking Spiolto might be different from patients taking only

NIS Protocol Page 27 of 43 BI Study Number: 1237-0109 c38644780-01

Proprietary confidential information © 2022 Boehringer Ingelheim International GmbH or one or more of its affiliated companies

maintenance therapies (so-called channelling) in terms of their baseline characteristics, which makes it difficult to interpret the results. To help put the results into perspective, we will compare the baseline characteristics between patients who initiated Spiolto and patients treated with other LAMA/LABAs to understand the potential channelling.

In a database study like this, we can only rely on the available information to define outcomes, exposure and covariates. Misclassification may happen during this process.

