10. DATA ANALYSIS

10.1 MAIN ANALYSIS

All variables, including patient characteristics, baseline measures, and outcomes, will be analyzed descriptively.

- For all analyses, variables will be reported as follows: Continuous variables (e.g., age) will be presented as means (with standard deviation, SD) and/or medians (with interquartile range, IQR), minimum, maximum.
- Categorical variables (e.g., sex) will be presented as absolute and relative frequencies.

We will first describe formation of the study cohort. Patient characteristics at baseline will be described using standard descriptive statistics. Absolute standardized differences (ASDs) will be used to compare the characteristics between the two groups, in which a >0.1 ASD indicates a meaningful difference.

As an objective of the study was to compare the clinical attributes of patients in each study group. The standardized difference will be used as a parameter to quantify the between-group differences for each clinical attribute. This is metric is commonly used in studies utilizing

Statistical and Epidemiological Analysis Plan (SEAP) for Non-Interventional Studies (NIS) Template

c40431892-01 Page 15 of 38

Proprietary confidential information © 2022 Boehringer Ingelheim International GmbH or one or more of its affiliated companies

secondary health data, in which a standardized difference of larger than 0.1 indicates a meaningful difference with respect to the clinical attribute between the two study groups.

For the analysis of primary outcome, the incidence rates of AEs during entire follow-up period will be calculated based on the following formula:

(Total number of patients in the Tio+Olo cohort experiencing an event of interest for the first time during the given time period) / (Total person-time at risk from current use of Tio+Olo during the given period)

[figure not shown]
Number of at-risk patients will be defined for specific adverse outcome of interest, taking into account whether it is a chronic condition for which patients with a prevalent condition are not considered at risk.

For the analysis of the primary outcome, individuals will be followed up from the index date until the earliest of the following

- 1) Outcome of interest
- 2) disenrollment;
- 3) the end of the study period;
- 4) death;
- 5) discontinuation of the index drug use as a lapse of 45 days without subsequent prescription;
- 6) adding ICS mono on top of Tio/Olo.

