	C01CA04, C01CA06, C01EB10, C01EB17, C07AA01, C07AA02,
	C07AA03, C07AA05, C07AA07, C07AA12, C07AA15, C07AA19,
	C07AB02, C07AB03, C07AB04, C07AB05, C07AB07, C07AB09,
	C07AB12, C08DA01, C08DB01
Heart failure	C01AA04, C01AA05, C01AA07, C01AA08, C01AB01, C01AC01,
medications	C01CA02, C01CA07, C01CE02, C01EB09, C01EB17, C03CA02,
	C03CA04, C03DA04, C07AG02, C09AA01, C09AA02, C09AA03,
	C09AA04, C09AA05, C09AA06, C09AA07, C09AA08, C09AA09,
	C09AA16, C09CA01, C09CA02, C09CA03, C09CA04, C09CA06,
	C09CA07, C09CA08, C09CA09
Nitrates	C01DA02, C01DA05, C01DA08, C01DA14
• Lipid-lowering	medications
Lipid Modifying	C10AA01, C10AA02, C10AA03, C10AA04, C10AA05, C10AA07,
Agents, Plain	C10AA08, C10AB01, C10AB02, C10AB03, C10AB04, C10AB05,
	C10AB06, C10AB09, C10AC01, C10AC02, C10AC03, C10AD01,
	C10AD02, C10AD03, C10AD06, C10AD, C10AX02, C10AX09,
	C10AX13, C10AX14, C10AX

Statistical and Epidemiological Analysis Plan (SEAP) for Non-Interventional Studies (NIS) Template

c40431892-01 Page 35 of 38

Lipid Modifying	C10BA01, C10BA02, C10BA03, C10BA05, C10BX03		
Agents, Combinations			
Blood glucose-lowering medications			
Insulins and analogues	A10AB01, A10AB03, A10AB04, A10AB05, A10AB06, A10AB30,		
	A10AC01, A10AC03, A10AC30, A10AD01, A10AD03,		
	A10AD04, A10AD05, A10AD06, A10AE01, A10AE04, A10AE05,		
	A10AE06, A10AE54		
	A10BA02, A10BA03, A10BB01, A10BB02, A10BB03, A10BB04,		
drugs, excl. insulins	A10BB05, A10BB07, A10BB08, A10BB09, A10BB12, A10BB31,		
	A10BD02, A10BD03, A10BD05, A10BD07, A10BD08, A10BD09,		
	A10BD10, A10BD11, A10BD13, A10BD14, A10BD, A10BD15,		
	A10BD19, A10BD20, A10BD21, A10BD24, A10BF01, A10BF02,		
	A10BG02, A10BG03, A10BH01, A10BH02, A10BH03, A10BH04,		
	A10BH05, A10BJ01, A10BJ02, A10BJ03, A10BJ05, A10BJ06,		
	A10BK01, A10BK02, A10BK03, A10BK04, A10BX01, A10BX02,		
	A10BX03, A10BX08		
Anticoagulants an	d antiplatelet agents		
Vitamin K antagonists	B01AA02, B01AA03		
Heparin group	B01AB01, B01AB04, B01AB05, B01AB06, B01AB10		
Platelet aggregation	B01AC04, B01AC05, B01AC06, B01AC07, B01AC09, B01AC11,		
inhibitors excl. heparin	B01AC13, B01AC16, B01AC17, B01AC21, B01AC22, B01AC23,		
	B01AC24, B01AC27, B01AC30		
Enzymes	B01AD01, B01AD02, B01AD04, B01AD10, B01AD11		
Direct thrombin	B01AE07		
inhibitors			
Direct factor Xa	B01AF01, B01AF02, B01AF03		
inhibitors			
Other antithrombotic	B01AX05		
agents			
• Antibiotic	 		

Statistical and Epidemiological Analysis Plan (SEAP) for Non-Interventional Studies (NIS) Template

c40431892-01 Page 36 of 38

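### The single cardiovascular row in the baseline comparison pools hypertension with cardiac disease, so a cardiac imbalance above the 0.1 threshold can go unflagged

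*SAP*

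**What the plan says.** Protocol 9.9 gives the purpose of the baseline comparison. It sets Tio/Olo initiators against "patients treated with other LAMA/LABAs to understand the potential channelling". The comparison is also the secondary objective (Protocol 8, SAP 5). The rule for reading it is in SAP 10.1: "a >0.1 ASD indicates a meaningful difference".

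SAP Appendix 4, row 2, defines cardiovascular disease as one variable, met by an inpatient diagnosis or repeated outpatient diagnoses. Its ICD-9 list starts "ICD9: 250.7, 401-405", continues "410-414, 425-428, 429.1", and also takes in 441, 442 and 458. The ICD-10 list is built the same way: I10-I13 and I15 stand beside ischemic, arrhythmia/conduction and I50 codes. Table 3 in SAP Annex 1 prints one line for this variable.

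Appendix 5 defines the cardiovascular drug rows. The heart-failure list contains "C09AA16, C09CA01, C09CA02, C09CA03, C09CA04, C09CA06", and the antihypertensive list contains "C09BB, C09CA01, C09CA02, C09CA03, C09CA04, C09CA06": the same C09CA codes in both.

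The protocol abstract names as a covariate "hospitalizations caused by exacerbation of heart failure, all-cause" hospitalizations. Protocol 9.3.3, SAP 7.2.2 and Table 3 have no heart-failure item. They list hospitalizations for COPD exacerbation and for all causes.

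**The concern.** Arrhythmia, supraventricular tachycardia, myocardial ischemia, nonfatal myocardial infarction and all-cause death are among the primary safety outcomes (SAP 7.2.1). To judge whether Tio/Olo was channelled towards or away from patients prone to these events, a reader needs to know how the cohorts compare on heart failure, arrhythmia and ischemic disease.

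One variable that is positive for any of these, or for hypertension alone, answers a different question. If hypertension is common, most patients are positive whatever their cardiac history, and a cardiac difference shrinks on the pooled scale. The threshold is applied to the pooled row, so the table could show no meaningful cardiovascular difference when heart failure differs clearly.

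The drug rows might be expected to fill the gap. However, a patient who takes one of the shared codes for hypertension alone is also counted under heart-failure or antiarrhythmic medication.

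**Working it through.** **Inputs.** The code lists come from SAP Appendices 4 and 5 and the 0.1 threshold from SAP 10.1. The documents give no prevalence for any of these conditions and no ASD formula, so there is no plan figure to reproduce. All prevalences below are assumptions, and the formula is the usual one for a binary variable.

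**1. Drug-code overlap (counted from Appendix 5).** The lists hold 116 distinct antihypertensive, 39 antiarrhythmic, 33 heart-failure and 4 nitrate codes.
- Heart failure and antihypertensive: 22 of 33 (67%). These are the C09AA and C09CA codes, C03CA02, C03CA04, C03DA04 and C07AG02.
- Antiarrhythmic and antihypertensive: 17 of 39 (44%). These are the C07AA and C07AB codes, C08DA01 and C08DB01.
- Heart failure and antiarrhythmic: 8 further shared codes. That leaves 33 − 22 − 8 = 3 codes found only in the heart-failure list and 39 − 17 − 8 = 14 found only in the antiarrhythmic list.
- Nitrates: no overlap with the other three lists.

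**2. Dilution in the pooled row.**

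ASD = |p1 − p2| / √{[p1(1 − p1) + p2(1 − p2)]/2}

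Pooled prevalence, taking the conditions as independent = 1 − (1 − HF)(1 − IHD)(1 − HTN), where HF is heart failure, IHD ischemic heart disease and HTN hypertension.

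Heart failure alone, 15% vs 8%: 0.07/√[(0.1275 + 0.0736)/2] = 0.07/0.317 = 0.22, which is flagged.

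Pooled, with IHD 10% and HTN 40% in both cohorts: p1 = 1 − 0.85 × 0.90 × 0.60 = 0.541 and p2 = 1 − 0.92 × 0.90 × 0.60 = 0.503. The ASD is 0.0378/0.499 = 0.076, which is not flagged.

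The same calculation elsewhere, with heart failure at 15% vs 8% throughout:

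| HTN (first vs second cohort) | Pooled ASD, IHD 10% | Pooled ASD, IHD 20% |
|---|---|---|
| 20% vs 20% | 0.105 (flagged) | 0.091 |
| 40% vs 40% | 0.076 | 0.068 |
| 60% vs 60% | 0.054 | 0.050 |
| 70% vs 70% | 0.044 | 0.041 |
| 43% vs 40% | 0.122 (flagged) | 0.110 (flagged) |
| 63% vs 60% | 0.105 (flagged) | 0.096 |

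If IHD also differs, 20% vs 14% (own ASD 0.16), with HTN balanced, the pooled ASD is 0.135 at HTN 40% (flagged), 0.098 at 60% and 0.081 at 70%.

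**3. A second parameterization.** Let c be the prevalence of any cardiac disease and h the share of non-cardiac patients who hold another qualifying code, equal in both cohorts. Pooled prevalence = c + (1 − c)h.
- Cardiac disease 10% vs 15% (ASD 0.152): pooled 0.087, 0.072, 0.060, 0.050 and 0.042 at h = 20, 30, 40, 50 and 60%. Never flagged.
- Cardiac disease 20% vs 30% (ASD 0.232): pooled 0.164, 0.141, 0.121, 0.103 and 0.087. Missed only at h = 60%.

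**4. The heart-failure drug row.** Assume heart failure 5% vs 10% (ASD 0.191), with 80% of heart-failure patients using a listed code. If 10, 20, 30 or 40% of the other patients also use one, the row's ASD is 0.097, 0.070, 0.053 or 0.040. At 10%, for example, the prevalences are 0.05 × 0.8 + 0.95 × 0.1 = 0.135 and 0.10 × 0.8 + 0.90 × 0.1 = 0.170.

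**The case against.** **The size of the masking is assumed and fragile.** This stands. Step 2 shows the pooled row crossing 0.1 at low hypertension prevalence with 10% ischemic disease, and in three of four cells when hypertension is 3 points higher in the cohort with more heart failure. Large cardiac differences usually get through as well. A reader might infer that the comparison will miss any cardiac channelling; neither the documents nor the arithmetic supports that.

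**Other Table 3 rows carry cardiac information.** This stands in part. Nitrates have no code overlap and could show an ischemic imbalance, and cerebrovascular disease has its own row. Anticoagulants/antiplatelets, the mean Charlson index and all-cause hospitalizations are not cardiac-specific. None isolates heart failure or arrhythmia.

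**The primary results are untouched.** This stands. A reader might infer that the adverse event rates are biased. They are single-cohort rates, and the visible plan neither compares outcomes with the other cohort nor adjusts for these covariates. For arrhythmia, myocardial ischemia, supraventricular tachycardia, myocardial infarction and stroke, SAP 7.2.1 also removes patients with the same condition in the baseline year. What remains is cross-condition influence, such as heart failure on arrhythmia, and mortality.

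**The heart-failure hospitalization item may be a slip.** It sits in the abstract where Protocol 9.3.3 and SAP 7.2.2 have COPD-exacerbation hospitalizations, which the abstract lacks. The documents do not show that a covariate was dropped, only that the texts disagree.

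**Part of the plan is not visible.** SAP pages after Table 3 and SAP 10.2 are blank or absent in the public copy, so the point covers only the visible tables and appendices.

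**Conclusion.** The point holds as a possibility, confined to the descriptive channelling comparison. The pooled definition and the code overlaps are facts of Appendices 4 and 5. The consequence rests on assumed prevalences, independence between conditions, and balance on everything except heart failure. On those terms, a heart-failure ASD of 0.22 appears in the pooled row as 0.068-0.076 at 40% hypertension and 0.041-0.044 at 70%, below the plan's threshold. The dilution grows as hypertension becomes more common. If hypertension is itself imbalanced, the pooled ASD can move either way. The change is still worth making, because the present row cannot tell a cardiac difference from a hypertension difference even when it is flagged.

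**What to change.** - Keep the pooled row. Add Table 3 rows, each with its own ASD, for hypertension, ischemic heart disease (410-414 and the matching I20-I25 codes), arrhythmia/conduction disorders (426-427; I44-I49) and heart failure (428; I50). Assign the codes within 402/404 and I11/I13 for hypertensive heart disease with heart failure to the heart-failure row, so that the hypertension row does not absorb them.
- Keep the existing drug rows, and state in a footnote that the heart-failure and antiarrhythmic rows share codes with the antihypertensive row and are not cardiac-specific. Do not strip the shared codes: only 11 of the 33 heart-failure codes would remain, 8 of them also antiarrhythmic codes, and patients treated only with the removed codes would be missed.
- Reconcile the abstract's heart-failure hospitalization covariate with Protocol 9.3.3, SAP 7.2.2 and Table 3, and state which item is intended.

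The cost is a longer table. Almost all the codes are already listed, and no new data are needed.
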